- Change in background treatment since the last visit (yes/no) [CRF p21]
- If yes, complete:
 - Background treatment was reduced (yes/no) [CRF p21]
 - If yes, reason (Remission or low level of activity/Tolerance problem/Other) [CRF p21]
 - Background treatment was stopped
 - If yes, reason (Remission or low level of activity/Tolerance problem/Ineffectiveness/Other) [CRF p21]
 - The basic treatment has been increased
 - If yes, reason (Ineffectiveness/Other) [CRF p21]
 - The background treatment has been replaced
 - If yes, reason (I neffectiveness/Intolerance/Other) [CRF p21]

NSAID treatments at M1

- Current oral NSAID intake (even occasional) (yes/no) [CRF p 22]

STAR – Statistical Analysis Plan
V3, June 2023

Page 39 of 96

Compliance with treatment at M4

- Level 1 followed correctly (yes/no) [CRF p43]
- Level 2 followed correctly (yes/no) [CRF p43]
- Level 3 followed correctly (yes/no) [CRF p43]
- If there is at least one “No” answer, specify:
- 1/ Has treatment with oral corticosteroids (prednisone, prednisolone, methylprednisolone) been received in addition to the treatment prescribed as part of the protocol since the last visit? (yes /no) [CRF p43]
 - If Yes, specify the reason:
 - Treatment of a disease flare-up documented by a rheumatologist (yes/no) [CRF p43]
 - Treatment of a flare-up by the attending physician (yes/no) [CRF p43]
 - Self-medication by the patient due to pain related to their rheumatoid arthritis (yes/no) [CRF p43]
 - Other, specify [CRF p43]
 - If Yes, do the prescribed dosages correspond to the rescue treatment provided for in the protocol? (yes /no) [CRF p43]
 - If Yes, Specify:
 - The number of attacks since the last visit [CRF p43]
 - If No, is it a one-off take? (yes /no) [CRF p43]
 - If yes, specify:
 - The number of attacks since the last visit [CRF p43]
 - Dose received (prednisone equivalent) (mg) [CRF p43]
 - The number of days of treatment [CRF p43]
 - If No, is it an addition of a long-term oral corticosteroid currently being taken? (yes /no) [CRF p43]
 - If Yes, specify:
 - daily dosage of prednisone or prednisone equivalent (mg/day) [CRF p43]
- 2/ Treatment with corticosteroids (other than hydrocortisone) IV or IM received in addition to the treatment prescribed as part of the protocol since the last visit? (yes /no) [CRF p44]
 - If Yes, specify:
 - The dose received (prednisone equivalent) (mg/day) [CRF p44]
 - The reason :
 - Treatment of a disease flare-up documented by a rheumatologist (yes/no) [CRF p44]

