
Taking at least one long-term oral corticosteroid during the protocol (yes/no)
	
From the variable Addition of a long-term corticosteroid orally to M4, M7, M9, M12, VAdd1 and Vadd2 [CRFp43, p68, p93, p110], Reason: Treatment of a flare-up of the disease objectified by a rheumatologist [CRFp43, p68, p93, p110], Reason: Treatment of a flare-up by the attending physician [CRFp43, p68, p93, p110] and Reason: Self-medication by the patient due to pain related to their polyarthritis rheumatoid [CRFp43, p68, p93, p110], we define two modalities
 
" If yes :
 
 • Addition of a long-term corticosteroid not orally to M4 = Yes 
 AND 
 ○ Reason: Treatment of a disease flare-up documented by a rheumatologist at M4 = Yes ○ OR Treatment of a flare-up by the attending physician at M4 = Yes ○ OR Self-medication by the patient due to pain related to their rheumatoid arthritis at M4 = Yes 
OR
 
 • Addition of a long-term corticosteroid not orally at M7 = Yes 
 AND 
 ○ Reason: Treatment of a flare-up of the disease documented by a rheumatologist at M7 = Yes ○ OR Treatment of a flare-up by the attending physician at M7 = Yes ○ OR Self-medication by the patient due to pain related to their rheumatoid arthritis at M7 = Yes 
OR
 
 • Addition of a long-term corticosteroid not orally at M9 = Yes 
 AND 
 ○ Reason: Treatment of a flare-up of the disease documented by a rheumatologist at M9 = Yes ○ OR Treatment of a flare-up by the attending physician at M9 = Yes ○ OR Self-medication by the patient due to pain related to his rheumatoid arthritis at M9 = Yes 
OR
 
 • Addition of a long-term corticosteroid not orally at M12 = Yes 
 AND

STAR – Statistical Analysis Plan
V3, June 2023

Page 69 of 96

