	
 ○ Reason: Treatment of a flare-up of the disease documented by a rheumatologist at M12 = Yes ○ OR Treatment of a flare-up by the attending physician at M12 = Yes ○ OR Self-medication by the patient due to pain related to their rheumatoid arthritis at M12 = Yes 
OR
 
 ● Addition of a long-term oral corticosteroid to VAdd1 = Yes 
AND
 
 ○ Reason: Treatment of a flare-up of the disease documented by a rheumatologist at VAdd1 = Yes ○ OR Treatment of a flare-up by the attending physician at VAdd1 = Yes ○ OR Self-medication by the patient due to pain related to their rheumatoid arthritis at VAdd1 = Yes 
OR
 
 ● Addition of a long-term oral corticosteroid to Vadd2 = Yes 
AND
 
 ○ Reason: Treatment of a flare-up of the disease documented by a rheumatologist at VAdd2 = Yes ○ OR Treatment of a flare-up by the attending physician at VAdd2 = Yes ○ OR Self-medication by the patient due to pain related to their rheumatoid arthritis at VAdd2 = Yes 
It will take the value "No" in all other cases.

Taking at least one attack corresponding to rescue treatment during the protocol (yes/no)
	
From the prescribed dosage variables, do they correspond to the rescue treatment provided for by the protocol [CRFp43, p68, p93, p110], the number of attacks since the last visit [CRFp43, p68, p93, p110], Reason: Treatment a flare-up of the disease documented by a rheumatologist [CRFp43, p68, p93, p110], Reason: Treatment of a flare-up by the attending physician [CRFp43, p68, p93, p110] and Reason: Self-medication by the patient for cause of pain related to rheumatoid arthritis [CRFp43, p68, p93, p110], we define two modalities:
 
" If yes :
 
 ● dosages correspond to the rescue treatment provided for in the protocol to be M4 = Yes ● AND The number of attacks since the last visit to M4 > 0 
AND
 
 ○ Reason: Treatment of a flare-up of the disease documented by a rheumatologist M4 = Yes

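### Secondary endpoint 4: the long-term oral corticosteroid component is coded as non-oral at the four scheduled visits, contradicting its own name and source variable

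*SAP*

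**What the plan says.** In the SAP's secondary endpoint analyses, section 4 builds the need for rescue glucocorticoid from five components joined by OR. The first is named "Taking at least one long-term oral corticosteroid during the protocol (yes/no"). Its derivation opens by naming the source variable, "Addition of a long-term corticosteroid orally to M4, M7, M9, M12, VAdd1 and Vadd2", taken from CRF p43, p68, p93 and p110.

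The conditions for Yes then differ by visit. Each also requires a flare-related reason (flare documented by a rheumatologist, flare treated by the attending physician, or self-medication for RA pain).

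- M4: "Addition of a long-term corticosteroid not orally to M4"
- M7: "Addition of a long-term corticosteroid not orally at M7"
- M9: "Addition of a long-term corticosteroid not orally at M9"
- M12: "Addition of a long-term corticosteroid not orally at M12"
- First additional visit: "Addition of a long-term oral corticosteroid to VAdd1", with the same oral wording at the second.

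All other cases are set to No. In the composite, a component that is No or missing counts towards No. The composite is compared between arms by a Chi2 or Fisher test at 0.05.

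**The concern.** The same derivation asks for opposite things at different visits. Read literally, it ignores a long-term oral corticosteroid added for a flare at any of the four scheduled visits, which is the event the component is named for, and counts it only at an unscheduled visit. Because the rule defaults to No, the error would leave no missing value or inconsistency to alert the analyst.

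Long-term resumption is an outcome the SAP expects: the end-of-study sheet lists it among the reasons for premature termination. What is at stake is an understated proportion in a secondary comparison that is formally tested.

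**Working it through.** The SAP gives no figure to reproduce here, so the check applies the rule as written to test records and then works out the effect on the proportions.

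**Step 1. Which CRF item is available.** The SAP itemises CRF p43 under compliance with treatment at M4. Within the question on oral corticosteroids, the long-term branch reads "If No, is it an addition of a long-term oral corticosteroid currently being taken". The other items in that block are IV or IM corticosteroids, infiltrations and additional hydrocortisone; none is a long-term non-oral item. IV/IM treatment also has its own component in endpoint 4. A non-oral meaning for this component therefore has no listed source and no gap to fill. The four CRF pages cited for the oral source variable are those of the four scheduled visits, where the condition says the opposite.

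**Step 2. Truth table.** One record per visit, with a flare reason of Yes at that visit:

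| Visit | Oral long-term added, rule as written | Oral long-term added, header variable used | Non-oral long-term added, rule as written |
|---|---|---|---|
| M4 | No | Yes | Yes |
| M7 | No | Yes | Yes |
| M9 | No | Yes | Yes |
| M12 | No | Yes | Yes |
| Additional visit 1 | Yes | Yes | No |
| Additional visit 2 | Yes | Yes | No |

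**Step 3. Does the composite recover the patient?** On CRF p43 the branches run in sequence: rescue dosage; if not, one-off course; if not, long-term addition. A record that reaches the long-term branch has answered No to the first two, so the two short-course components are also No at that visit. The patient is still counted as Yes overall if any of these applies:

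- a rescue or one-off course for a flare at another visit;
- IV/IM treatment for a flare;
- a qualifying infiltration (as printed, that component needs a count above 1 for Yes and 0 for No, so exactly one injection does not qualify);
- a long-term oral addition recorded at an additional visit.

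Only patients with none of these are lost.

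**Step 4. Effect on the comparison.** Let p1 and p2 be the true proportions needing extra prednisone, and s1 and s2 the shares of those patients lost under Step 3. The literal rule reports p1(1 − s1) and p2(1 − s2). If s1 = s2 = s, the reported difference is (p1 − p2)(1 − s), so a fraction s of both the events and the difference disappears. The SAP gives neither p nor s. With assumed proportions of 40% and 20%:

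| Assumed share s | Reported proportions | Reported difference |
|---|---|---|
| 0 | 40% vs 20% | 20 points |
| 10% | 0.40 × 0.9 = 36% vs 0.20 × 0.9 = 18% | 18 points |
| 30% | 0.40 × 0.7 = 28% vs 0.20 × 0.7 = 14% | 14 points |
| 50% | 0.40 × 0.5 = 20% vs 0.20 × 0.5 = 10% | 10 points |

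**Step 5. Primary endpoint.** The primary endpoint uses its own derivations. Modality 1 takes oral corticosteroid and hydrocortisone use directly from the M12 items, and the count of days on oral glucocorticoid for other reasons treats the long-term item as oral. The disputed wording does not enter.

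**The case against.** The strongest reply is that nobody would program this. The name, source variable, additional-visit lines and cited CRF pages all say oral. A programmer looking for a non-oral long-term field would not find one in the listing and would probably fall back on the oral field. The SAP reads as a rough translation in several places, and a slip copied into four parallel lines fits that. This largely stands: the misclassification is conditional on literal coding, and a slip is the likeliest explanation, although the source-language text is not available to confirm it. It does not make the text harmless. The SAP requires a signed amendment for any deviation, so an analyst who codes the evident intention departs from the approved rule, and one who follows the rule misclassifies patients.

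A second reply is that few patients need be lost. Flare symptoms are meant to trigger an additional visit, where the oral condition applies, and other components may catch the patient. This also stands, and is why the size is given as a range over an assumed share.

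A third is that the endpoint list describes endpoint 4 as a short rescue treatment, so long-term restarts may not belong to it. The corresponding objective is wider, and the composite explicitly includes the long-term oral component, so under the SAP's own operative definition these patients count.

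A reader might also infer that the comparison could reverse. The documents do not support that. With equal shares the difference only shrinks. With the assumed 40% vs 20%, reversal needs 0.40(1 − s1) < 0.20(1 − s2); even with s2 = 0, that means s1 above 50%. Nothing in the SAP suggests such an imbalance.

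**Conclusion.** The contradiction is certain: four of the six conditions in this component oppose its name, its source variable and the other two conditions. Its effect on results is conditional. Under literal coding, patients whose only qualifying event is long-term oral prednisone recorded at a scheduled visit are counted as not needing extra prednisone. The endpoint 4 proportions are then too low. If the lost share is similar in both arms, the difference shrinks by about that share, for example 10% to 50% for assumed shares of 10% to 50%; the documents give no rate.

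It would go too far to infer that endpoint 4 will be biased whatever the program does, or that the trial's main conclusion is at risk. The first depends on how the wording is coded, and the primary endpoint does not use this rule. The point concerns one of five OR terms in one secondary endpoint. It still deserves correction, because it is an operative rule feeding a formal test.

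**What to change.** In section 4 of the secondary endpoint analyses, replace the non-oral condition at M4, M7, M9 and M12 with the oral variable already named at the head of the derivation, equal to Yes (CRF p43, p68, p93, p110), matching the two additional visits. Leave the flare-reason conditions unchanged. Check that the program reads the oral field at all six visits.

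The cost is four short wording changes under the SAP's own signed amendment procedure, plus a check of the code. It needs no new data and changes no clinical rule. It is best made before the database is frozen and the groups are unblinded.

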	Divide by number of items answered: _____				=F Subscale score
 To derive a FACIT-F Trial Outcome Index (TOI): Score range: 0-108					
$\frac{\text{_____}}{\text{(PWB score)}} + \frac{\text{_____}}{\text{(SWB score)}} + \frac{\text{_____}}{\text{(EWB score)}} + \frac{\text{_____}}{\text{(FWB score)}} + \frac{\text{_____}}{\text{(FS score)}} = \text{_____} = \text{FACIT-F TOI}$					
 To Derive a FACT-G total score: Score range: 0-108					
$\frac{\text{_____}}{\text{(PWB score)}} + \frac{\text{_____}}{\text{(SWB score)}} + \frac{\text{_____}}{\text{(EWB score)}} + \frac{\text{_____}}{\text{(FWB score)}} = \text{_____} = \text{FACT-G Total score}$					
 To Derive a FACIT-F total score: Score range: 0-160					
$\frac{\text{_____}}{\text{(PWB score)}} + \frac{\text{_____}}{\text{(SWB score)}} + \frac{\text{_____}}{\text{(EWB score)}} + \frac{\text{_____}}{\text{(FWB score)}} + \frac{\text{_____}}{\text{(FS score)}} = \text{_____} = \text{FACIT-F Total score}$					
 https://www.facit.org/measures-scoring-downloads/facit-f-scoring-downloads					

STAR – Statistical Analysis Plan
V3, June 2023

Page 51 of 96

EQ-5D

- Mobility (I have no problem getting around on foot/I have problems getting around on foot/I am forced to stay in bed)
[CRF p31, 55]
- Personal autonomy (I have no problem taking care of myself/I have problems washing or dressing myself/ I am unable to wash or dress myself on my own [CRF p31, 55]
- Current activities (examples: work, studies, housework, family activities or leisure activities) (I have no problem carrying out my current activities/I have problems carrying out my current activities/I am unable to carry out my current activities)
[CRF p31, 55]
- Pain/discomfort (I have no pain or discomfort/I have moderate pain or discomfort/I have extreme pain or discomfort)
[CRF p31, 55]
- Anxiety / Depression (I am neither anxious nor depressed/I am moderately anxious or depressed/I am extremely anxious or depressed)
[CRF p31, 55]

Visual analog scale

- Your health today (from 0 to 100) [CRF p32, 56]

Calculation method

■ Matrice de pondération

Dimension	Niveau de réponse	Score de préférence	
Mobilité	1		0
	2	u1	0,15
	3		0,37
Autonomie de la personne	1		0
	2	u2	0,21
	3		0,32
Activités courantes	1		0
	2	u3	0,16
	3		0,19
Douleurs / gênes	1		0
	2	u4	0,11
	3		0,26
Anxiété / dépression	1		0
	2	u5	0,09
	3		0,20
Constante	Si au moins une dimension est au niveau 3	N3	0,17

Source : Chevalier 2010

■ Fonction de scorage

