--	---

STAR – Statistical Analysis Plan
V3, June 2023

Page 74 of 96

	
treatment prescribed as part of the protocol at Vadd1 = Yes
 
AND
 
 ○ Reason: Treatment of a flare-up of the disease documented by a rheumatologist in Vadd1 = Yes ○ OR Treatment of a flare-up by the attending physician at Vadd1 = Yes 
OR
 
 ● Was treatment with corticosteroids (other than hydrocortisone) IV or IM received in addition to the treatment prescribed as part of the protocol at Vadd2 = Yes 
AND
 
 ○ Reason: Treatment of a flare-up of the disease documented by a rheumatologist in Vadd2 = Yes ○ OR Treatment of a flare-up by the attending physician at Vadd2 = Yes 
It will take the value “No” in all other cases.

Patient having received at least one corticosteroid infiltration during the protocol (yes/no)
	
From the variables: Total number of infiltrations received in relation to RA over the duration of post-randomization follow-up [Derived Variable], we define two modalities:
 
" If yes :
 
 ● Total number of infiltrations received in relation to RA over the duration of post-randomization follow-up > 1 
" Not if :
 
 ● Total number of infiltrations received in relation to RA over the duration of post-randomization follow-up = 0

Need for GC salvage treatment during protocol (yes/no)
	
From the following derived variables: Taking at least one long-term oral corticosteroid during the protocol (yes/no) [Derived Variable], Taking at least one attack corresponding to rescue treatment during the protocol (yes /no) [Derived Variable], Taking at least one short GC therapy not corresponding to rescue treatment for the entire duration of the study (yes/no) [Derived Variable], Taking at least one treatment by IV or IM corticosteroid during the protocol (yes/no) [Derived Variable], Patient having received at least one corticosteroid infiltration during the protocol (yes/no) [Derived Variable], we define two modalities:
 
" If yes :
 
 ● Taking at least one long-term oral corticosteroid during the protocol = Yes ● OR Taking at least one attack corresponding to rescue treatment during the protocol = Yes

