STAR – Statistical Analysis Plan
V3, June 2023

Page 75 of 96

	
 • OR Taking at least one short GC therapy not corresponding to rescue treatment for the entire duration of the study = Yes • OR Taking at least one IV or IM corticosteroid treatment during the protocol = Yes • OR Patient having received at least one corticosteroid infiltration during the protocol = Yes 
" Not if :
 
 • Taking at least one long-term oral corticosteroid during the protocol = No or missing • AND Taking at least one attack corresponding to rescue treatment during the protocol = No or missing • AND Taking at least one short GC therapy not corresponding to rescue treatment for the entire duration of the study = No or missing • AND Taking at least one IV or IM corticosteroid treatment during the protocol = No or missing • AND Patient having received at least one corticosteroid infiltration during the protocol = No or missing
--	---

The proportion of patients supplemented with prednisone will be compared in the two groups using a Chi2 test after verification of the application conditions: theoretical numbers greater than 5. In the event that the application conditions are not respected, an exact test of Fisher will be used.

The significance threshold for the tests is set at 0.05.

STAR – Statistical Analysis Plan
V3, June 2023

Page 76 of 96

5) Proportion of patients who received intra-articular injections

Proportion of patients who required intra-articular or periarticular GC injection during RA-related protocol.

Variable name	Derivations
Intra-articular injections (yes/no)	
From the variables “ Total number of infiltrations received in relation to RA over the duration of post-randomization follow-up ” [Derived variable], we define two modalities:
 
" If yes :
 
 • “ Total number of infiltrations received in relation to RA over the duration of post-randomization follow-up ” ≥ 1 
" Not if :
 
 • “ Total number of infiltrations received in relation to RA over the duration of post-randomization follow-up ” = 0

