The proportion of patients having received intra-articular injections will be compared in the two groups using a Chi2 test after verification of the application conditions: theoretical numbers greater than 5. In the event that the application conditions are not respected , a Fisher exact test will be used.

The significance threshold for the tests is set at 0.05.

Off-protocol analysis:

For exploratory purposes, without implementing a statistical test, we will carry out a descriptive analysis of secondary judgment criteria no. 4 and no. 5 in a combined manner.

Variable name	Derivations
Intra-articular injections and Need for short GC salvage treatment (yes/no)	
From the variables “ Need for a short rescue treatment with GC during the protocol ” [Derived variable] and “ Intra-articular injections ” [Derived variable], we define two modalities:
 
" If yes :
 
 • “ Need for short GC salvage treatment during protocol ” = Yes OR • “ Intra-articular injections ” = Yes 
" Not if :
 
 • “ Need for short GC salvage treatment during protocol ” = No AND • “ Intra-articular injections ” = No

The results will be presented using numbers and percentages.

STAR – Statistical Analysis Plan
V3, June 2023

Page 77 of 96

6) Proportion of patients who had at least one relapse during the protocol

Proportion of patients with a flare-up confirmed by the clinician. In the event of flare-up symptoms, the patient will have an additional visit to their center. For DAS28 >3.2, a surge will be confirmed. A flare will also be diagnosed if the DAS28 is >3.2 at any scheduled visit.

Variable name	Derivations

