- In the event of missing data at one or more visits, we will impute the non-missing values of the randomization group from which the patient came at the visit in question by the median value.

Patient FLARE scores should have a large number of missing data (questionnaires poorly completed during follow-up). These scores present will be described in each group using the mean, standard deviation, median and interquartile range. In the event of missing data on one of the items, the value of the missing item will be replaced by the median value of the item at the visit concerned according to the patient's randomization group.

No bivariate analysis will be performed on these scores.

STAR – Statistical Analysis Plan
V3, June 2023

Page 79 of 96

8) Proportion of patients in remission or at low activity level according to the DAS28 at 7 and 12 months

Proportion of patients in remission and with low disease activity at 7 months and one year. Patients with a DAS28 < 2.6 will be considered in remission, patients with a DAS28 between 2.6 and 3.2 will be considered in LDA.

The DAS28 formula is as follows:

$$\text{DAS28} = (0.56 * \text{sqr}(\text{TJC})) + (0.28 * \text{sqr}(\text{SJC})) + (0.7 * \text{ln}(\text{VS})) + (0.014 * \text{GH})$$

Where **TJC** = Number of painful joints [CRFp72, p114]
SJC = Number of swollen joints [CRFp72, p114]
VS = the sedimentation rate [CRFp84, p126]
GH = overall health represents the patient's assessment of disease activity on a scale of 0 to 100 where 100 corresponds to maximum activity [CRFp81, p123].
 The DAS28 is calculated automatically in the e-CRF.

Variable name	Derivations
Remission according to DAS28 (Yes No)	
From the DAS28 scores at M7 and M12 (variable present in the database or programmed), we define two modalities:
 
 • " If yes : 
 ○ DAS28 < 2.6 • " Not if : 
 ○ DAS28 ≥ 2.6 
For each of times M7 and M12, a variable will be created using the same methods.

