Low level of activity according to DAS28 (yes/no)	
From the DAS28 scores at M7 and M12 (variable present in the database or programmed), we define two modalities:
 
 • " If yes : 
 ○ DAS28 ≥ 2.6 and < 3.2 • " Not if : 
 ○ DAS28 ≥ 3.2 ○ OR if DAS28 > 2.6 
For each of times M7 and M12, a variable will be created using the same methods.

Remission or low level of activity according to DAS28 (Yes No)	
From the variables " Remission according to DAS28 " and " Low activity level according to DAS28 " [Derived variable], we define two modalities:
 
" If yes :
 
 • " Remission according to DAS28 " = Yes OR • " Low activity level according to DAS28 " = Yes 
" Not if :
 
 • " Remission according to DAS28 " = No AND • " Low level of activity according to DAS28 " = No 
For each of times M7 and M12, a variable will be created using the same methods.

STAR – Statistical Analysis Plan
V3, June 2023

Page 80 of 96

The proportion of patients in remission or at a low level of activity will be compared in the two groups using a Chi² test after verification of the application conditions: theoretical numbers greater than 5. In the event that the application conditions are not not respected, a Fisher exact test will be used.

The significance threshold for the tests is set at 0.05.

STAR – Statistical Analysis Plan
V3, June 2023

Page 81 of 96

9) HAQ-DI score at 4, 7 and 12 months

Functional impairment assessed by the Health Assessment Questionnaire (HAQ) at baseline, 4, 7 months and one year.

The HAQ will be calculated at baseline [CRFp25-26], at 4 [CRFp49-50], 7 months [CRFp74-76] and one year [CRFp116-117], and is expressed as continuous data.

The HAQ-DI SCORE at inclusion 4, 7 and 12 months will be compared in the two groups using a Student t test if the application conditions are met and a non-parametric Mann-Whitney Wilcoxon test otherwise.

The significance threshold for the tests is set at 0.05.

STAR – Statistical Analysis Plan
V3, June 2023

Page 82 of 96

10) RAID score at 4, 7 and 12 months

Patient-reported outcomes assessed by the Rheumatoid Arthritis Impact of Disease (RAID) questionnaire at baseline, 4, 7 months, and 1 year.

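### Derivation rules for secondary endpoints 4, 6 and 8 contradict their own definitions: one injection alone is coded as no rescue, the low-disease-activity Yes and No rules overlap, and the flare rule and a DAS28 input do not match the text

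*SAP*

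**What the plan says.** All four rules are in the SAP's chapter on the analyses of the secondary criteria.

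- **Endpoint 4 (section 4).** The component named "Patient having received at least one corticosteroid infiltration during the protocol (yes/no" is Yes if "Total number of infiltrations received in relation to RA over the duration of post-randomization follow-up > 1" and No if "Total number of infiltrations received in relation to RA over the duration of post-randomization follow-up = 0". The composite is No when every component is No or missing, including "Patient having received at least one corticosteroid infiltration during the protocol = No or missing". Section 5 (endpoint 5) codes the same count Yes from 1 upwards.
- **Endpoint 8 (section 8).** The text places LDA between 2.6 and 3.2. The derivation codes Yes from 2.6 to below 3.2, and No at 3.2 or above "OR if DAS28 > 2.6". The tested remission-or-LDA variable is built from this one.
- **Endpoint 6 (section 6).** The text says: "A flare will also be diagnosed if the DAS28 is >3.2 at any scheduled visit". The derivation reads only the CRF yes/no question on a documented flare, which uses 3.2 or above, and counts a blank answer as No.
- **DAS28 formula (section 8).** The global term GH is the patient's assessment of disease activity on 0 to 100, "where 100 corresponds to maximum activity [CRFp81, p123". The patient questionnaire listed under the data at inclusion collects that assessment on 0 to 10. The EQ-5D scale is listed as "Your health today (from 0 to 100) [CRF p32, 56". The SAP says that the e-CRF calculates DAS28, and it also allows a programmed value.

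**The concern.** These are the rules a programmer will follow, and the SAP requires a signed amendment for any deviation, so they should not be repaired silently. Endpoint 4 and the remission-or-LDA variable are each tested at 0.05. If a rule contradicts its own label, or gives different answers depending on line order, the reported proportion is not the pre-specified one. The LDA band matters in this trial because entry requires a DAS28 of 3.2 or lower, so patients may well be in that band at M7 and M12.

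**Working it through.** The plan gives no figure to reproduce here. The check is to apply each rule as written.

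**(a) Endpoint 4, patient with no other rescue component**

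| RA injections | Component in endpoint 4 | Composite, endpoint 4 | Endpoint 5 |
|---|---|---|---|
| 0 | No | No | No |
| 1 | no value | No | Yes |
| 2 | Yes | Yes | Yes |
| 3 | Yes | Yes | Yes |

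Only the row for one injection is wrong. The share of such patients is not given. Assuming 5%, 10% or 15% of the planned 51 per arm: 0.05 × 51 = 2.6, 0.10 × 51 = 5.1, 0.15 × 51 = 7.7 patients per arm.

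**(b) LDA in endpoint 8**

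| DAS28 | Meets LDA Yes | Meets LDA No |
|---|---|---|
| below 2.6 | no | no |
| exactly 2.60 | yes | no |
| 2.61 to 3.19 | yes | yes |
| 3.2 or above | no | yes |

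Of the 60 two-decimal values from 2.60 to 3.19, 59 meet both rules. If the No line runs last, a DAS28 of 3.0 becomes LDA No and remission No, so remission-or-LDA is No. If the Yes line runs last, the tested variable is correct. Patients in remission get no LDA value, but the tested variable is still Yes for them through remission. If 10%, 30% or 50% of patients lie in the overlap (assumed), the tested proportion is 10, 30 or 50 points too low under the No-last order and unchanged under the other.

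**(c) Flare in endpoint 6.** A scheduled visit with DAS28 above 3.2 and the CRF question answered Yes is counted. With the question answered No or left blank, the stated definition gives a flare and the derivation does not count that visit. At exactly 3.2, the text gives no flare, the CRF question gives a flare, and the LDA derivation gives not LDA.

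**(d) Source of GH.** CRF pages printed in the SAP:

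| Item | M4 | M7 | M12 |
|---|---|---|---|
| Joint counts | 47 | 72 | 114 |
| RAID | 51 | 76 | 118 |
| FACIT-F | 52-54 | 77-79 | 119-121 |
| EQ-5D items | 55 | 80 | printed as 27 |
| EQ-5D scale | 56 | not printed | not printed |
| Synacthen test | 60 | 85 | 127 |

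Apart from the M12 EQ-5D entry, these M7 pages are the M4 page + 25 and these M12 pages are the M4 page + 67. The EQ-5D scale would then be on 56 + 25 = 81 and 56 + 67 = 123, exactly the two pages cited for GH. The patient disease-activity item is on p48 at M4, and 48 + 25 = 73, a page the SAP does cite for patient-rated pain at M7.

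Possible effect: GH enters as 0.014 × GH, so a wrong field can shift DAS28 by at most 0.014 × 100 = 1.4. Suppose the scale runs from worst to best health (an assumption) and a value of 70 or 80 replaces an activity of 30 or 20. The shift is then 0.014 × (70 − 30) = 0.56 or 0.014 × (80 − 20) = 0.84, against an LDA band of 3.2 − 2.6 = 0.6. Using the 0-to-10 item unscaled would lower DAS28 by up to 0.014 × (100 − 10) = 1.26.

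**The case against.** The strongest reply is that the intent is clear everywhere. The variable's name says at least one, the LDA range is given in words, GH is correctly defined in words, and the e-CRF computes DAS28. A careful programmer would get all of it right. That limits the likely harm, but it does not make the written rules correct.

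Several stronger readings are tempting, and the SAP does not support them:

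- *The exploratory combination of endpoints 4 and 5 is also wrong because of the injection rule.* It is not: it is Yes if either endpoint is Yes, and endpoint 5 catches the single injection.
- *Every LDA patient is misclassified.* Exactly 2.60 meets only the Yes rule, and the others are miscoded only if the No line runs last.
- *Flares seen at visits are dropped.* The CRF question is itself defined by DAS28 and is read at M4, M7, M9, M12 and both additional visits. A flare is lost only where the answer is No or blank.
- *DAS28 is computed from the EQ-5D scale.* No text labels p81 or p123 as that scale. The page offsets are strong evidence, but SAP page references contain slips: EQ-5D at M12 is p27, HAQ at M7 is printed as p74-76 and so overlaps RAID on p76, and the flare question at M4 is on p34 in one place and p45 in another. The SAP also does not state which way the scale runs.
- *The primary endpoint is affected.* Its injection criterion is more than two and does not use these variables.

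One further objection stands and affects the remedy. The secondary objectives and endpoint list define endpoint 4 as extra prednisone for flares, or a short rescue glucocorticoid treatment, with injections listed separately as endpoint 5. Once the component reads 1 or more, endpoint 4 contains every endpoint 5 event, and the exploratory combination equals endpoint 4.

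**Conclusion.** The point holds for secondary endpoints 4, 6 and 8, with unequal strength. The injection rule is wrong as written and always miscodes a patient with exactly one RA injection and no other rescue. The LDA No rule is wrong as written, and its effect ranges from none to the whole share of patients at 2.61 to 3.19, depending on coding order. The flare derivation omits part of its own definition and uses a different threshold, and the loss is conditional on how the CRF question was answered. The GH page reference is a probable error to be verified. It matters only if DAS28 is programmed from those pages or the e-CRF uses that field. The missing 0-to-100 rescaling is a separate gap in the formula's specification. All patient shares and scale values used for size are assumptions, since the SAP gives none.

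**What to change.** 1. **Endpoint 4:** change the Yes rule from more than 1 to 1 or more, to match the variable's name and endpoint 5. Reconcile whether injections belong in endpoint 4 at all, given its stated definition. If they stay, note that the exploratory combination adds nothing.
2. **Endpoint 8:** make LDA No equal to DAS28 below 2.6, or 3.2 and above, which complements the existing Yes rule. Settle one convention for exactly 3.2 and use it for both LDA and flare.
3. **Endpoint 6:** add the recorded visit DAS28 to the derivation, with a single threshold, and state how a patient with missing visits is classified.
4. **DAS28:** verify the GH page reference, cite the patient disease-activity item, state the multiplication by 10, and check the e-CRF DAS28 against a recalculation from its components.

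The cost is four short text corrections in a signed SAP amendment, one recalculation check, and one decision on the content of endpoint 4. No new data are needed, and the changes are best made before unblinding.
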